Alcohol Research Center
University of Connecticut School of Medicine
Department of Psychiatry, MC-2103
[name]
[name]

Project Title: Dutasteride treatment for the reduction of heavy drinking.

Study PI: [name]

Co-investigators: [name], [name], [name]

Abstract

FDA approved pharmacotherapy options for alcohol use disorders remain limited, with only three currently approved compounds (disulfiram, naltrexone and acamprosate). Recent studies highlight the potential for medications used for the treatment of other indications to be examined for the treatment of alcohol use disorders. Study of additional agents, particularly those that act through novel mechanisms, is needed to expand the range of pharmacotherapy options for alcohol use problems. Extensive preclinical studies indicate that neuroactive steroids mediate important effects of alcohol and support the examination of neuroactive steroid modulators as treatment options for alcohol use problems. Dutasteride, a widely prescribed medication for benign prostatic hypertrophy, blocks a key step in the production of neuroactive steroids and represents a promising candidate for treatment of alcohol use disorders. This study will use a randomized placebo controlled design to examine the safety and efficacy of dutasteride to reduce drinking among a sample of 160 men with hazardous levels of alcohol use. It will additionally examine the potential moderation of dutasteride treatment effects by a common missense polymorphism in a neuroactive steroid biosynthetic enzyme (3 α HSD type 2; aka 17 β HSD type 5) that we have previously reported to be associated with alcohol dependence. Identification of genetic predictors of medication response offers the potential for matching alcohol treatment medications with those most likely to respond.

Specific Aims.

Alcohol has multiple biological effects on the nervous system which each represent potential targets for pharmacotherapy of alcohol use disorders. Animal studies indicate that alcohol induced generation of GABA_A receptor neuroactive steroid agonists mediate several of alcohol's effects. Pharmacologic blockade of neuroactive steroid production has been reported to reduce alcohol intake in animal models. Dutasteride, a widely used medication to treat benign prostatic hypertrophy is an irreversible inhibitor of 5-alpha reductase (5AR) enzymes required for the production of neuroactive steroids, and thus has potential as a pharmacologic treatment for alcohol use disorders in humans. In a recently completed placebo controlled study in humans of the effects of a single 4 mg dose of dutasteride given 2-4 days prior to a moderate dose of alcohol (0.8 gr/kg body weight) we found that while dutasteride has limited effects on subjective responses to a standard battery of alcohol effect questionnaires, it produced a significant reduction in drinking during the first two weeks following dutasteride, but not placebo medication treatments for subjects with a history of moderate drinking. The proposed study will extend these findings by examining the safety and efficacy of dutasteride for alcohol use disorders in human subjects by conducting a 12-week randomized placebo controlled trial of dutasteride for the reduction of alcohol use in male problem drinkers.

Aim 1. To examine the safety and efficacy of dutasteride in helping problem drinkers to reduce or stop drinking. 160 men with hazardous levels of alcohol use (≥ 24 standard drinks / week) will be randomly assigned to treatment with either dutasteride or placebo for 12-weeks. Alcohol use will be reported daily via an interactive voice response system. Biological markers (gamma glutamyl transferase, carbohydrate deficient transferin) will be used as secondary measures of change in alcohol use and a serum neuroactive steroid metabolite 3 α -androstaneadiol glucuronide will be used to monitor inhibition of 5 α -reductase enzyme activity by dutasteride. We hypothesize that 1 mg / day dutasteride will be well tolerated by heavy drinkers, will produce $\geq 85\%$ reduction in serum markers of 5 α -reductase enzyme activity and that compared with placebo will result in a greater reduction in the number of heavy drinking days and drinks per week.

Aim 2. To examine the durability of effects of dutasteride treatment on drinking and heavy drinking during a six-month post-treatment follow-up. Dutasteride elimination kinetics have a saturable component such that following weeks of daily dosing the elimination half-life of dutasteride gradually increases producing a delayed (weeks) recovery of 5AR activity. We hypothesize that reductions in drinking and heavy drinking during the treatment period will persist to a greater degree in dutasteride vs. placebo treated patients.

Aim 3. To examine whether treatment response is moderated by a common genetic variation, H5Q, in the neuroactive steroid biosynthetic enzyme 3 α -hydroxysteroid dehydrogenase gene *AKR1C3* that has been associated with alcohol dependence. *AKR1C3* genotype will be included among urn randomization variables for assignment to drug vs. placebo groups. We hypothesize that dutasteride treatment will result in greater reductions in drinking for subjects who are homozygous for the *AKR1C3* alcohol risk allele (38% of subjects) compared with protective allele carriers.

Aim 4. To examine the potential effects of dutasteride on the relations among daily mood and daily events on drinking and heavy drinking, and the potential effects of dutasteride on daily reports of alcohol subjective effects to identify potential intermediate effects of dutasteride on treatment outcomes. We hypothesize that within-person associations between daily mood or daily events and drinking and heavy drinking will be moderated by dutasteride.

Project Title: Dutasteride treatment for the reduction of heavy drinking.

Research Strategy

A. Significance.

Alcohol use disorders are highly prevalent, frequently chronic and have significant adverse effects on the health and quality of life of alcoholic individuals and their families. Recent large scale household surveys indicate that of US adults who use alcohol, 5% meet criteria for alcohol dependence while an additional 20% of drinkers could be considered problem drinkers who meet at least one criterion for an alcohol use disorder (McBride et al. 2009). Many if not most problem drinkers do not seek treatment and are often more interested in reducing rather than stopping drinking. Although problem drinkers can be identified using brief screening tools in primary care settings, primary care providers are often hesitant to intervene using psychological treatments for problem drinkers and may be more willing to provide medical therapies for alcohol use disorders. Pharmacotherapy options for alcohol use disorders remain limited, with only three currently FDA approved compounds (disulfiram, naltrexone and acamprosate). Recent studies highlight the potential for medications approved for the treatment of other indications (e.g. topiramate, ondansetron, zonisamide, baclofen) to be applied to treatment of alcohol use disorders [reviewed in (Edwards et al. 2011)]. Study of additional agents, particularly those that act through novel mechanisms, is needed to expand the range of pharmacotherapy options for alcohol use problems. The neuroactive steroid system represents such a novel mechanism, and dutasteride a widely prescribed medication that blocks a key step in the production of neuroactive steroids represents a promising candidate for treatment of alcohol use disorders. This study will examine the safety and efficacy of dutasteride to reduce drinking among heavy drinkers. It will additionally examine the potential moderation of treatment effects of dutasteride by a common missense polymorphism in a neuroactive steroid biosynthetic enzyme which we have shown to be associated with alcohol dependence (Milivojevic et al. 2011). Identification of genetic predictors of medication response offers the potential for matching alcohol treatment medications with those more likely to respond (Kranzler and Edenberg 2010; Johnson et al. 2011; Kranzler et al. 2011). While this study will examine only men, as dutasteride is currently not FDA approved for use in women due to the potential for adverse effects on fetal development of male external genitalia, men represent an important target population as alcohol use disorders are significantly more common in men than women.

B. Innovation.

The primary innovation of the proposed study is the examination of a novel therapeutic mechanism, inhibition of 5 α -reduced neuroactive steroid production, to reduce alcohol use among heavy drinkers using a currently approved and well tolerated medication, dutasteride. Dutasteride is somewhat unique in having a long-half life following repeated administration providing a natural prolonged effect and slow self taper following end of treatment. Additional innovative components include examination of a strong candidate genetic polymorphism for moderation of dutasteride effect and use of daily self reports of mood, life events, alcohol effects and alcohol use via an interactive voice response system (IVR) to allow examination of moderating effects of dutasteride on relationships between mood, daily events and drinking as well as explore potential effects of dutasteride on subjective alcohol effects in a natural setting.

Neuroactive steroids and alcohol effects.

An extensive body of pre-clinical studies support the hypothesis that endogenous neuroactive steroids produced in response to alcohol mediate some of the behavioral and electrophysiological effects of alcohol [reviewed in (Kumar et al. 2009)]. 5 α reduced 3 α -hydroxy-pregnane and 3 α -hydroxy-androstane neuroactive steroids are endogenous, highly potent (i.e., active at nanomolar concentrations), positive allosteric modulators of GABA_A receptor function (Paul and Purdy 1992) that are produced both peripherally and in the brain. They increase the frequency and the duration of the open state of GABA-gated chloride channels (Belelli et al. 2005), contributing to neuroactive steroid's anticonvulsant (Belelli et al. 1989; Reddy 2004), antinociceptive (Nadeson and Goodchild 2001), antidepressant (Khisti et al. 2000; Uzunova et al. 2006) and anxiolytic (Bitran et al. 1991; Wieland et al. 1991; Akwa et al. 1999) properties.

In rat models, alcohol increases levels of neuroactive steroids in plasma and brain of intact animals and in brain slice preparations (Barbaccia et al. 1999; Morrow et al. 1999; VanDoren et al. 2000; O'Dell et al. 2004; Sanna et al. 2004). Blockade of ethanol-induced increases in neuroactive steroids in rats using the 5AR inhibitor finasteride attenuates several behavioral effects of alcohol (VanDoren et al. 2000; Hirani et al. 2002; Hirani et al. 2005) and blocks effects of alcohol on GABA_A currents in brain slice preparations (Sanna et al. 2004). Other studies have examined the effects of neuroactive steroids and their inhibitors on alcohol self-administration in rodents. In mice and rats trained to self-administer 10% ethanol, treatment with low doses of

the endogenous GABA_A neurosteroid agonist allopregnanolone (5 α -pregnan-3 α -ol-20-one) (Ford et al. 2005) or the synthetic neurosteroid agonist ganaxolone (Besheer et al. 2010) increase alcohol self administration. In contrast treatment with the GABA_A inhibitory neuroactive steroid epipregnanolone (5 β -pregnan-3 β -ol-20-one) reduces alcohol self-administration in rats (O'Dell et al. 2005). Additionally, blockade of neuroactive steroid production by the 5AR inhibitor finasteride attenuates acquisition of alcohol preference in mice (Ford et al. 2008) and reduces the self-administration of alcohol in mice previously training to self-administer ethanol (Ford et al. 2005) as well as in naïve mice (Ramaker et al. 2011). Together these results from pre-clinical studies suggest that alcohol related changes in neuroactive steroid levels or patterns of metabolism contribute to the reinforcing aspects of alcohol in self-administration paradigms and that blockade of these processes by inhibitors of 5AR may be useful in reducing alcohol consumption in humans.

Data from human studies supporting neuroactive steroids as mediators of alcohol effects are more limited. In humans, the plasma concentration of allopregnanolone has been reported to be increased following severe intoxication (Torres and Ortega 2003; Torres and Ortega 2004), but not moderate intoxication (Holdstock et al. 2006; Pierucci-Lagha et al. 2006; Porcu et al. 2009). Recently (see preliminary studies) we have reported that polymorphisms in two key neuroactive steroid biosynthetic enzymes, 5AR, type I (encoded by *SRD5A1*), and 3 α -hydroxysteroid reductase type 2 (encoded by *AKR1C3*) are associated with AD (Milivojevic et al. 2011).

Finasteride which has been widely used as a pharmacological tool in animal studies of neuroactive steroids blocks both type I and II 5AR in rodents but in humans, finasteride at typical clinical doses blocks only type II 5AR, the isoenzyme of 5AR most abundant in prostate and skin but absent in adult brain. Dutasteride, a second FDA approved 5AR inhibitor for treatment of prostatic hyperplasia, irreversibly inhibits of both type I (brain, adrenal and liver) and type II (liver, skin and prostate) 5AR enzymes at clinically relevant dosages, leading to a greater reduction in 5 α -dihydrotestosterone (DHT) levels compared with finasteride without suppressing testosterone (Clark et al. 2004). This broader 5AR inhibition profile together with good tolerability and safety record make dutasteride an excellent candidate for reducing drinking in humans given the effects of finasteride in reducing alcohol self-administration in mice (Ford et al. 2005). The sequential actions of 5AR and the *AKR1C3* gene product 3 α -HSD, which are the focus of this study, are illustrated in Figure 1 for the metabolism of testosterone to DHT and to the neuroactive steroid 3 α ,5 α -androstane-3 α ,17 β -diol (aka 3 α ,5 α -androstaneadiol).

[figure not shown]

Figure 1. Biosynthesis of DHT and the neuroactive steroid 3 α ,5 α -androstanediol from testosterone. Dutasteride blocks 5AR, the first enzyme in this pathway. The *AKR1C3* gene product 3 α -HSD type 2 reduces DHT to 3 α ,5 α -androstanediol. A common polymorphism in *AKR1C3* is associated with AD (C.2.b). 3 α ,5 α -androstanediol is metabolized to the water soluble elimination product 5 α -androstan-3 α ,17 β -diol,17-glucuronide (3 α -diolG) which will be assayed to measure 5AR inhibition by dutasteride. 3 α ,5 α -androstanediol can also be produced by the 17 β reduction (also catalyzed by the *AKR1C3* gene product) of 3 α ,5 α -androsterone. As illustrated for 3 α ,5 α -androstanediol, 5AR and 3 α -HSD are sequentially required for the generation of 3 α ,5 α -androsterone from the precursor androstanedione.

Relevance of this proposal to the Alcohol Research Center at the University of Connecticut School of Medicine. This project is an extension of prior research on the pharmacotherapy of alcohol dependence (AD) and heavy drinking that has been conducted at the UConn ARC for the past 20 years including clinical trials of fluvoxamine, fluoxetine, nefazadone, naltrexone, zonisamide and topiramate. This project will focus on reduction of drinking in heavy drinkers by a novel pharmacologic approach, manipulation of neuroactive steroid production. Recruitment for this study will benefit from implementation at all UConn clinical sites beginning in mid-2012 of Screening, Brief Intervention, and Referral for Treatment (SBIRT) for alcohol use problems for which [name] of the UConn ARC has been one of the innovators (Babor et al. 2007). Dissemination and training in use of SBIRT is the focus of [name] component of the UConn ARC P60 renewal application. Identification of genetic associations with AD and alcohol use risk factors has been a focus of research for UConn ARC investigators during the past decade. The current study is in part motivated by recent ARC supported research which identified common polymorphisms in neuroactive steroid biosynthetic enzyme genes

as being associated with AD (section C.2.b.). Finally, this project employs daily monitoring technologies refined by ARC investigators in prior treatment trials. The study benefits from the involvement of ARC investigators with complementary backgrounds, [name] (psychiatrist with experience in prior ARC pharmacologic treatment trials of AD and in human genetic studies), [name] (psychological determinants of problem drinking and daily process investigations), [name] (internist and smoking cessation clinical research expert who has been a collaborator on prior ARC pharmacologic treatment studies) and [name] (biostatistician with prior experience in clinical trial data analysis).

C. Research Approach

[figure not shown]
C.1. Preliminary Studies.

C.1.a. Effects of dutasteride on drinking in a naturalistic setting (Covault et al., 2012).

In a recently completed study funded by an R01 to [name], we used dutasteride to block de novo production of 5 α -reduced neuroactive steroids to examine the potential role of neuroactive steroids on the acute effects of alcohol in male social drinkers. In a secondary analysis as part of this study we examined the naturalistic use of alcohol by subjects between monthly laboratory sessions as a function of dutasteride vs. placebo drug. In this study, subjects participated in 4 laboratory sessions at one-month intervals in which pre-treatment with dutasteride (4 mg) or placebo was paired 2-4 days later with a moderate dose of alcohol (0.8 gr/kg) or placebo alcohol in a laboratory setting. Two groups of males aged 21-45 were recruited: low intensity drinkers with at most 1 episode of heavy drinking (≥ 5 SDs) per month and moderate drinkers with ≥ 3 episodes of heavy drinking per month. The pharmacologic effect of dutasteride was measured by assay of serum 5 α -androstan-3 α ,17 β -diol,17-glucuronide (aka 3 α -androstane diol glucuronide or 3 α -diolG) as a biochemical measure of 5AR inhibition. 3 α -diolG is the primary metabolic excretion product of 3 α ,5 α -androstane neuroactive steroids, that has been shown to decrease in parallel with DHT following finasteride treatment in men (Rittmaster et al. 1989; Gormley et al. 1990). A single 4 mg loading dose of dutasteride produced a 70% (S.D.=14%) reduction in 3 α -diolG levels as well as similar reductions in plasma levels of the neuroactive steroids allopregnanolone and 3 α ,5 α -androstane diol measured by GC/MS. Dutasteride was well tolerated in combination with a moderate dose of alcohol and compared to placebo, reduced self reported sedative effects of alcohol. Other subjective effects were minimally impacted by dutasteride pre-treatment.

We additionally collected data on alcohol use between laboratory sessions both as a measure of study safety (i.e., to ensure that participation did not lead to increased hazardous drinking) and to examine whether exposure to single doses of dutasteride influenced drinking in the 3 weeks following each alcohol lab session. As illustrated in Figure 2, among 29 moderate drinkers (mean standard drinks/week=14) we observed a significant reduction in the number of heavy drinking days (HDD) during the first and second week following dutasteride exposures and in the total number of drinks per week in the first week after dutasteride but not placebo dosing. These results suggest that blocking neuroactive steroid production in moderate drinkers reduces reinforcing aspects of alcohol in a time-limited fashion following a single 4 mg dose of dutasteride resulting in reduced levels of drinking (Cohen's $d=0.36$ for HDD/wk1 and $d=0.37$ for SDs/wk1). No significant effect was seen for low-intensity drinkers ($n=33$), perhaps because of a floor effect for this group (baseline mean SDs/wk = 4). These results parallel pre-clinical studies reporting a reduction in alcohol self-administration in mice following 5AR inhibition with finasteride (Ford et al. 2005; Ramaker et al. 2011) and strongly support the rationale for the proposed clinical trial of dutasteride to reduce drinking in heavy drinkers.

Figure 2. Weekly TLFB data following laboratory sessions with dutasteride ($n=42$) or placebo ($n=42$) pretreatment for 29 moderate-intensity male drinkers. Paired t-test statistics for post-lab drinking compared with 90-day TLFB baseline data. **A.** HDD/wk - significant decreases observed for weeks 1 and 2 following dutasteride lab, ** $t= -4.15$, $p<0.001$; * $t= -2.29$, $p=0.028$. **B.** SD/wk significant decrease for week 1 following dutasteride lab, ** $t= -3.12$, $p=0.003$.

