Drinking outcomes: For 27 subjects completing the 8 week active phase as of July 1 (excluding 7 subjects with abstinence from outset (3 dutasteride and 4 placebo subjects) mixed model analysis showed a main effect of baseline drinking ($p=0.005$), study week ($p=0.001$), AKR1C3*2 genotype ($p=0.029$) and a trend for genotype by drug interaction ($p=0.56$) such that subjects gradually reduced drinking during the 8 weeks with AD risk allele homozygotes showing the highest level of drinking and the greatest benefit from dutasteride compared with placebo condition. For the 19 subjects who have reaced the 2 month post-treatment follow-up there was a significant drug x time interaction with a 48% decrease in SDs/w for dutasteride and a 39% decrease for placebo compared with baseline drinking [mixed model $F(124)=4.68$, $p=0.032$; effect size $d=0.30$].

Summary. These pilot study results support our ability to recruit and enroll subjects for the proposed study and indicate that dutasteride is well tolerated in alcoholic subjects with no effect of dutasteride on serum testosterone levels in the face of an 85% reduction in the 5AR enzyme metabolite 3 α -diolG. Preliminary

drinking outcomes indicate that participants reduced drinking during the study period and that dutasteride may have greatest benefit for AKR1C3*2 alcohol dependence risk C-allele homozygotes.

C.2. RESEARCH DESIGN AND METHODS

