Efficacy analyses will be performed using linear mixed models implemented in SPSS. Medication group will be treated as a factor and treatment week as a continuous covariate. An interaction term between medication group and week will be used to evaluate the efficacy of dutasteride compared to placebo in reducing drinking behavior over time. Pretreatment drinking will be controlled for using TLFB drinking data for the month prior to screening as a covariate. Treatment goal (stop vs. reduce drinking) will also be included as baseline covariate. The robustness of results will be evaluated by running the model under three different conditions: 1) all provided information, 2) only completers, and 3) imputation where missing days are coded as HDDs for subjects who fail to complete treatment.

For aim 3, analysis of drinking outcome variables will be repeated by including genotype at the *AKR1C3* rs12529 polymorphism as an additional between-subject factor.

C.8.a.3 Examination of daily measures.

Multilevel models will be used to examine the relations among daily measures of mood, daily event triggers and the frequency of drinking and of heavy drinking (level 1 measures) and their moderation by medication (level 2 measure). To examine how the within-person processes vary across individuals (i.e., cross-level medication interactions), the level 1 parameters are considered as outcomes in the level 2 model. Of specific interest is how the level 1 slopes (e.g., the associations between mood or daily event triggers and heavy drinking) vary as a function of experimental condition (dutasteride vs. placebo). Control variables (baseline heavy drinking, depression symptom score, baseline AD symptom severity) will also be included in level 2 predictive models. The utility of each level 2 predictor will be determined by the significance tests of the level 2 partial regression slopes.

C.8.b. Sample size considerations:

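### The Aim 4 daily models have no study-time term, so if mood or events drift while the arms' drinking trends diverge, the medication interaction test can signal moderation that is not there

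*Combined protocol and SAP*

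**What the plan says.** The hypothesis is in Specific Aims, Aim 4: "We hypothesize that within-person associations between daily mood or daily events and drinking and heavy drinking will be moderated by dutasteride". The purpose given there is to identify possible intermediate effects of dutasteride on outcome.

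The analysis is in C.8.a.3. For level 1 it says: "Multilevel models will be used to examine the relations among daily measures of mood, daily event triggers and the frequency of drinking", and it adds heavy drinking as an outcome. Medication enters at level 2 as a moderator of the level 1 slopes. The covariates are these: "Control variables (baseline heavy drinking, depression symptom score, baseline AD symptom severity) will also be included in level 2 predictive models". The decision rule is: "The utility of each level 2 predictor will be determined by the significance tests of the level 2 partial regression slopes". No day, week or weekend variable is named there, and no other section supplies one for Aim 4.

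The efficacy model in C.8.a.2 is different: "Medication group will be treated as a factor and treatment week as a continuous covariate", and "An interaction term between medication group and week will be used to evaluate the efficacy of dutasteride compared to placebo".

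The pilot report in C.1.c found an effect of study week (p=0.001), described as "subjects gradually reduced drinking during the 8 weeks".

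**The concern.** A within-man slope of drinking on mood uses all of the covariation between the two series over 84 days, slow as well as day-to-day. If mood improves over the weeks while drinking falls, part of the slope reflects two trends that happen to run together. When the drinking trend is the same in both arms, that contamination is the same in both arms and cancels from the medication contrast. When drinking falls faster in one arm, it does not cancel, and the difference is read as the drug changing the mood-drinking link.

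The three listed controls cannot help, because each is constant within a man. The plan allows for arm-specific drinking trends in its efficacy test but not in Aim 4. What is at stake is the mechanism conclusion: a drug that only lowers drinking gradually could be reported as weakening mood-driven or event-driven drinking.

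**Working it through.** **The plan's own figure.** C.8.b gives 80% power for d=0.45 with 80 per arm at alpha 0.05. A two-sided two-sample calculation gives 81.2%, so the figure reproduces. C.8.b states no power or error rate for Aim 4, so there is no Aim 4 figure to reproduce.

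**Inputs from the documents**
- 80 completers per arm (C.8.b) and 12 weeks = 84 daily reports, 90% of them completed (C.1.c).
- Pilot baseline of 46 drinks/week, SD 20 (C.1.c).
- Design gap: 0.45 × 20 / 7 = 1.29 drinks/day.
- Pilot gap, from "a 48% decrease in SDs/w for dutasteride and a 39% decrease for placebo compared with baseline drinking": (0.48 − 0.39) × 46 / 7 = 0.59 drinks/day.

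**Assumptions (the documents give no figures)**
- Linear mood drift of 0.25, 0.5 or 1 within-man SD over 12 weeks, equal in both arms.
- Daily residual SD of 3 drinks.
- Mood slope of 0.3 drinks per SD (SD 0.3 between men), with the same mean in both arms.
- Personal 12-week drinking trends with SD 2 drinks/day.

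**Size of the bias by hand.** Scale time to run from 0 to 1 over treatment, so its variance is about V = 1/12. With mood drift δ (in within-man SD) and an end-of-treatment gap g between the arms' linear trends, the spurious arm difference in slope is about −δgV / (1 + δ²V). For g = 1.29:
- δ = 0.25: 0.25 × 1.29/12 / 1.005 = 0.027
- δ = 0.5: 0.5 × 1.29/12 / 1.021 = 0.053
- δ = 1: 1.29/12 / 1.083 = 0.099

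Simulation gave −0.026, −0.055 and −0.102. At δ = 1 the artefact is about a third of the assumed true link (0.102 / 0.3 = 34%).

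**False-positive rate of medication × mood.** There is no true moderation. The test is at nominal 5% with person-clustered standard errors and 1,000 runs per cell.

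| Trend gap at week 12 | Model | 0.25 SD | 0.5 SD | 1 SD |
|---|---|---|---|---|
| 0.59 drinks/day | as written | 5.6% | 5.5% | 10.8% |
| 0.59 drinks/day | + common week | 4.1% | 8.9% | 8.8% |
| 1.29 drinks/day | as written | 7.5% | 12.4% | 25.2% |
| 1.29 drinks/day | + common week | 6.7% | 10.8% | 28.5% |
| either | + week and medication × week | 4.7-4.8% | 4.8-5.1% | 4.7-4.9% |

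A separate simulation at the 1.29 gap gave 7%, 11% and 25% as written, and 4-6% with week plus medication × week or with a man-specific week slope.

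If d=0.45 is instead the 12-week average of a linearly growing effect, the week-12 gap is 2 × 1.29 = 2.57 drinks/day. The rates as written are then 10.4%, 31.1% and 71.5%.

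**Conditions under which nothing happens**
- No mood drift, with trends diverging by the pilot gap: 4.5%.
- Mood drift of 0.5 or 1 SD with identical drinking trends: 5.4% and 5.0%.
- A weekend effect common to both arms (mood +0.5 SD, +2 drinks): 5.3%. The rate rose, to 27.5%, only when the weekend drinking effect was made to differ by arm (+2 versus +1).

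**Shape of onset.** The 12-week average gap is held at 1.29 drinks/day. Rates are for drifts of 0.25, 0.5 and 1 SD.
- Immediate and constant effect: 5.7%, 4.9%, 5.1%.
- Two-week ramp: 4.4%, 6.9%, 10.2%.
- Four-week ramp: 5.5%, 12.1%, 23.7%.
- Linear over 12 weeks: 10.8%, 30.3%, 72.7%.

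These runs use a linear model for daily drinks. The binary heavy-drinking model may give different figures.

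**The case against.** A reader might infer that Aim 4 is biased whenever Aim 1 is true. The documents do not support that. Aim 1 predicts only a greater reduction in heavy drinking days and drinks per week. An early drop that then holds steady satisfies it and leaves no difference in trend within treatment. Early onset is plausible on the plan's own evidence: the single-dose study in C.1.a saw its effects in weeks 1 and 2, and C.3.a.2 expects most of the enzyme inhibition within about four weeks. This stands, and it removes any unconditional claim. It does not remove the conditional one, because C.8.a.2 tests medication by week and so allows for gradual divergence.

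A reader might also take the 48% versus 39% contrast as evidence that the arms diverge during treatment. C.1.c reports it for 19 men who had reached the two-month post-treatment follow-up. For the eight-week active phase C.1.c reports no drug by week effect. The 0.59 drinks/day gap is therefore only a convenient scale, and at that gap the inflation is small.

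A missing weekend term might look like an equal fault. It is not: a weekend effect common to both arms leaves the moderation test at its nominal level.

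Two further points stand. No document gives a drift in mood or events, so the larger rates rest on assumption. Detrending also has a price, because it removes any genuine slow covariation between mood and drinking.

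**Conclusion.** The concern holds conditionally. C.8.a.3 omits study time from the Aim 4 models. The medication interaction test is exposed when two things happen together: a daily predictor drifts over the 12 weeks, and the arms' drinking trends diverge during treatment. For drifts of 0.25, 0.5 and 1 within-man SD, the false-positive rate is about 7%, 11-12% and 25% if d=0.45 is the week-12 gap reached linearly, and about 5-11% at 0.59 drinks/day. It stays at 5% if either condition fails, including when the drug effect is immediate and constant. The figures depend on the assumed drift, daily variance and onset shape. The point is worth acting on because the setting is one that the plan's own efficacy hypothesis allows, and a false result would be read as mechanism.

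**What to change.** In C.8.a.3, state that every Aim 4 model includes centred study week at level 1 and medication by week (or a man-specific week slope), and that medication by mood and medication by event are tested from that model. A common week term alone should not be used as the remedy, because it leaves the difference between the arms' trends in place. A weekend indicator is optional. It bears on the moderation test only if it carries its own medication interaction.

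The cost is a sentence or two in the analysis plan and a few model terms. Week follows from the dates of the daily IVR calls, so no new data are needed. The downside is that slow, week-level covariation between mood and drinking no longer counts towards the estimated link. The model without time terms can be reported as a sensitivity analysis so that readers see both.
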